## 6.1.1 Outpatient Visit for ECR Assessment and Other Site Procedures

Outpatients must return to the site for a face-to-face visit with study personnel  $96 \pm 24$  hours (i.e., 72 to 120 hours) after the first dose of study drug. Study personnel will inform Outpatients as to the timing of this required study site visit in the course of the daily telephone contacts.

The purpose of this site visit is to assess CABP signs and symptoms which will be used to programmatically determine the ECR, as well as to perform other procedures that cannot be done by telephone (i.e., ECG, blood samples for PK analysis, blood samples for safety assessments, vital signs, and physical examination).

ECGs and blood samples for PK analysis must be performed within specified time windows before and after study drug administration. Therefore, it is **critical** that the subject be instructed to not take their first dose of study drug at home that day, rather to bring all their blister packs (used and unused) to the study site. The dose associated with the outpatient visit for ECR assessment and other site procedures will be taken under supervision of study personnel. In addition, as discussed in Sections 5.4 and 6.17, study personnel will remind subjects regarding adherence to the food and supplement restrictions when scheduling this visit.

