# 9.2 Sample Size Determination

A total of 738 subjects will be randomized in a ratio of 1:1 (lefamulin:moxifloxacin) resulting in 369 subjects in the lefamulin arm and 369 in the moxifloxacin arm in this study. The total number of subjects included in this study is sufficient to achieve the primary and secondary study objectives based on statistical considerations.

Retrospective analyses of clinical study data for patients with CABP of varying severity as well as 2 recent clinical trials in CABP indicate the point estimates for an ECR responder at Days 3-5 range from 72% to 81% (FDA, 2011; Barrera et al., 2016; Cempra, 2015; Oldach et al., 2015). Thus, it is reasonable to assume that in a prospective study of subjects with CABP, the proportion of subjects who are responders for ECR at  $96 \pm 24$  hours post first dose of study drug will be approximately 79%.

The primary efficacy analysis variables used for NI analyses for the Marketing Authorization Application (MAA) to the EMA will be the proportion of subjects with an IACR of Success at TOC in the mITT and CE-TOC Analysis Sets. In recent clinical studies, IACR success rates at the TOC Visit in the CE Analysis Set ranged from 77% to 93% (Cempra, 2015) and in the ITT Analysis Set ranged from 85% to 89% depending on the antibiotics under study and the severity of the CABP. Based on these data, an 85% IACR success rate in the CE-TOC Analysis Set was chosen for determination of the sample size. The success rate is expected to be about 5% lower in the mITT Analysis set. It is expected that <1% of subjects will be excluded from the mITT Analysis Set and thus, the sample size determination assumes the same number of subjects in the ITT and mITT Analysis Sets.

Utilizing an anticipated ECR responder rate of 79% in the ITT Analysis Set, a 1:1 randomization ratio, a two-sided alpha of 0.025, and a continuity corrected Z-test with unpooled variance, a sample size of 738 subjects (369 subjects in the lefamulin group and 369 in the moxifloxacin group) provides 90% power to establish the NI of lefamulin to moxifloxacin for ECR using a NI margin of 10.0% at the ECA. Assuming an IACR success of 80% and 85% in the mITT and CE-TOC Analysis Sets, respectively, and a clinical evaluability rate of 80%, there is 91% power for demonstration of NI for IACR at the TOC Visit using a 10% NI margin.

The calculated power in each analysis set for the primary and secondary outcomes is provided in Table 6 below.

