### 6.1 Primary Efficacy Outcome: Early Clinical Response

The primary efficacy outcome is the percentage of subjects with an ECR of responder at 96 ± 24 hours after the first dose of study drug in the ITT Analysis Set. Symptom definitions for the assessment are shown in [Table 2](#). Subjects will be programmatically defined as a **responder** if the following 4 criteria are met:

- Alive;
- Improvement in at least 2 of the 3 or 4 cardinal symptoms of CABP the subject presented with at baseline. Improvement is defined as a decrease by at least 1 level of severity;
- No worsening of any of the 4 cardinal symptoms of CABP. Worsening is defined as an increase by at least 1 level of severity for any symptom;
- Did not receive a concomitant antibiotic for the treatment of CABP up through the assessment of the cardinal symptoms of CABP.

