**Table 2. Symptom Assessment for Early Clinical Response Assessment**

Symptom	Absent (0)	Mild (1)	Moderate (2)	Severe (3)
Dyspnea	Resolution (to pre-CABP baseline) or absence of dyspnea	Dyspnea on exertion (eg, climbing stairs)	Dyspnea with normal/routine activities (eg, walking)	Dyspnea at rest or requiring oxygen therapy
Cough	Resolution (to pre-CABP baseline) or absence of cough	Transient, does not interfere with normal activity	Frequent, interferes with normal activity or sleep	Constant, interferes with most or all activity or sleep
Production of purulent sputum	Resolution (to pre-CABP baseline) or absence of sputum production	Sputum production rarely causes difficulty or distress	Sputum production often causes difficulty or distress	Constant difficulty with sputum production
Chest pain	Resolution or absence of chest pain related to CABP	Transient, does not interfere with normal activity	Frequent, interferes with normal activity or sleep	Constant, interferes with most or all activity or sleep

Subjects will be programmatically defined as a **non-responder** if any of the following are met:

- Did not show an improvement in at least 2 of the 3 or 4 cardinal symptoms of CABP the subject presented with at baseline. Improvement is defined as a decrease by at least 1 level of severity; or
- Worsening of any of the 4 cardinal symptoms of CABP. Worsening is defined as an increase by at least 1 level of severity for any symptom; or
- Received a concomitant antibiotic for the treatment of CABP up through the assessment of the cardinal symptoms of CABP, or if no assessment was completed, up to 120 hours after the first dose of study drug (or randomization if the subject did not receive study drug); or
- Died from any cause up through the assessment of the cardinal symptoms of CABP, or if no assessment was completed, up through Study Day 5.

If more than 1 assessment of symptoms is obtained in the 96 ± 24 hour window, the following rules apply:

- Use the latest assessment of symptoms conducted in person occurring in the 96 ± 24 hour window
- If no assessment was conducted in person, use the latest assessment of symptoms conducted via a telephone call occurring in the 96 ± 24 hour window

If no assessment of symptoms (either in person or by telephone) was conducted in the 96 ± 24 hour window, the following rules apply:

- Use the latest assessment of symptoms conducted in person occurring 60 to <72 hours after the first dose of study drug

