## 7.0 STATISTICAL METHODS

### 7.1 Sample Size

A total of 738 subjects will be randomized in a ratio of 1:1 (lefamulin:moxifloxacin) resulting in 369 subjects in the lefamulin arm and 369 in the moxifloxacin arm in this study. The total number of subjects included in this study is sufficient to achieve the primary and secondary study objectives based on statistical considerations.

Retrospective analyses of clinical study data for patients with CABP of varying severity as well as 2 recent clinical trials in CABP indicate the point estimates for an ECR responder at Days 3-5 range from 72% to 81% (FDA, 2011; Barrera et al., 2016; Cempra, 2015; Oldach et al., 2015). Thus, it is reasonable to assume that in a prospective study of subjects with CABP, the proportion of subjects who are responders for ECR at  $96 \pm 24$  hours post first dose of study drug will be approximately 79%.

The primary efficacy analysis variables used for NI analyses for the Marketing Authorization Application (MAA) to the EMA will be the proportion of subjects with an IACR of Success at TOC in the mITT and CE-TOC Analysis Sets. In recent clinical studies, IACR success rates at the TOC Visit in the CE Analysis Set ranged from 77% to 93% (Cempra, 2015) and in the ITT

Analysis Set ranged from 85% to 89% depending on the antibiotics under study and the severity of the CABP. Based on these data, an 85% IACR success rate in the CE-TOC Analysis Set was chosen for determination of the sample size. The success rate is expected to be about 5% lower in the mITT Analysis Set. It is expected that <1% of subjects will be excluded from the mITT Analysis Set and thus, the sample size determination assumes the same number of subjects in the ITT and mITT Analysis Sets.

Utilizing an anticipated ECR responder rate of 79% in the ITT Analysis Set, a 1:1 randomization ratio, a one-sided alpha of 0.025, and a continuity corrected Z-test with unpooled variance, a sample size of 738 subjects (369 subjects in the lefamulin group and 369 in the moxifloxacin group) provides 90% power to establish the NI of lefamulin to moxifloxacin for ECR using a NI margin of 10.0%. Assuming an IACR success of 80% and 85% in the mITT and CE-TOC Analysis Sets, respectively, and a clinical evaluability rate of 80%, there is 91% power for demonstration of NI for IACR at the TOC Visit using a 10% NI margin.

The calculated power in each analysis set for the primary and secondary outcomes is provided in [Table 7](#).

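### When the primary endpoint falls back to a 60 to <72 h assessment, SAP 6.1 read literally ignores later CABP antibiotics and contradicts itself on later deaths

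*SAP*

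**What the plan says.** - **Protocol window.** Early Clinical Response (ECR) is assessed at 96 ± 24 h. Protocol 6.1.1 spells this out for outpatients: "i.e., 72 to 120 hours) after the first dose of study drug".
- **Protocol rules.** The antibiotic criterion in Protocol 9.4.1 has no cut-off at the assessment. Under Protocol 9.8 a missing field needed for ECR makes the subject Indeterminate, which counts as non-response.
- **SAP fallback.** When nothing was assessed in the window, in person or by telephone, SAP 6.1 says: "Use the latest assessment of symptoms conducted in person occurring 60 to <72 hours after the first dose of study drug". A telephone assessment in the same 12 hours is the next choice.
- **SAP antibiotic criterion for a responder.** "Did not receive a concomitant antibiotic for the treatment of CABP up through the assessment of the cardinal symptoms of CABP".
- **SAP antibiotic criterion for a non-responder.** It has the same cut-off, with one extension: "or if no assessment was completed, up to 120 hours after the first dose of study drug".
- **SAP death criterion for a non-responder.** It is built the same way, with Study Day 5 as the limit when there is no assessment.
- **SAP vital status for a responder.** The subject must be alive; no date is attached.

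SAP 7.6 assigns Indeterminate by reference to the Section 6.1 time frame, which includes the fallback. SAP 6.3.2 (ECR plus vital signs) repeats the cut-offs and refers back to 6.1 for the assessment rules. SAP 9.0 does not list the fallback as a change from the protocol.

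**The concern.** A fallback subject has a completed assessment, so on the literal wording the look-ahead to 120 h is switched off. An antibiotic for CABP given after the fallback assessment then neither blocks response nor triggers non-response. An assessment made before the protocol window opens overrides a failure recorded inside it, and the SAP gives no reason for this.

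This is the primary endpoint, and it is derived by program, so the text must give one answer for every subject. If late antibiotic use differs between arms, the rule removes more failures from the arm that has more of them and pulls a true difference toward zero. That direction is anti-conservative for non-inferiority (NI).

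None of the four sensitivity analyses in SAP 8.5.2 would show it. Two change the stratification. One recodes indeterminates and one recodes non-responders with less than 48 h of drug; subjects classed as responders through the fallback are neither.

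**Working it through.** **1. Classification under SAP 6.1.** All four subjects have no assessment at 72–120 h.

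| Subject | Responder list | Non-responder list | Result |
|---|---|---|---|
| Improved at 65 h, CABP antibiotic at 80 h | All four criteria met | Not triggered, read literally | Responder |
| No assessment, CABP antibiotic at 80 h | Improvement not shown | Triggered (before 120 h) | Non-responder |
| Improved at 65 h, dies at 80 h | Turns on when the subject must be alive | Not triggered, read literally | Unresolved |
| No assessment, dies at 80 h | Not met | Triggered (by Study Day 5) | Non-responder |

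Under the protocol the first subject is a non-responder either way: through the antibiotic, or as Indeterminate because in-window symptoms are missing.

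The two SAP limits also differ. Study Day 5 is a calendar day. If the first dose is at 14:00, Day 5 ends 120 − 14 = 106 h later, before the 120 h antibiotic limit.

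**2. The plan's own power.** Inputs from SAP 7.1: "anticipated ECR responder rate of 79% in the ITT Analysis Set", 369 per arm, "using a NI margin of 10.0" percentage points, and "a one-sided alpha of 0.025, and a continuity corrected Z-test with unpooled variance".

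- SE = √(2 × 0.79 × 0.21 / 369) = 0.0300
- Power = Φ((0.10 − 1/369)/SE − 1.96) = 0.9005, which matches the stated 90%.

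Protocol 9.2 instead says "a two-sided alpha of 0.025". Taken literally that gives 0.842, so the SAP wording is the one used here.

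**3. Size per subject.** 1/369 = 0.27 points of one arm's rate. The documents do not say how many subjects will use the fallback or how many of those will have a later event. Assume 0.5–3% of an arm use it and 5–50% of those have an event by 120 h:

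- Low end: 369 × 0.005 × 0.05 = 0.09 subjects, 0.025 points.
- High end: 369 × 0.03 × 0.50 = 5.5 subjects, 1.5 points.

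Both ends overstate the effect, because only subjects already improved, with no symptom worse, at 60 to <72 h can be misclassified.

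**4. Effect on the NI decision.** Lower limit = d − 1.96 × SE − 1/369, with moxifloxacin at 292/369 (79.1%) and reclassification in the lefamulin arm only.

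| Lefamulin responders | Difference (points) | Lower limit | NI |
|---|---|---|---|
| 292 (equal rates) | 0 | −6.13% | met |
| 287 (5 reclassified) | −1.36 | −7.56% | met |
| 282 (10 reclassified) | −2.71 | −8.98% | met |
| 279 | −3.52 | −9.83% | met |
| 278 | −3.79 | −10.11% | not met |

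One subject decides the result only at the last step.

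**5. Type I error if only lefamulin is lifted.** True rates 69% and 79%; a lift q is added to the 69%. The one-sided error is 0.0205 at q = 0, 0.025 at 0.27 points and 0.042 at 1 point.

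**6. Misclassification in both arms.** If the same fraction f of failures is erased in each arm, a true difference D becomes D(1 − f). With 369 − 292 = 77 failures and 3 erased, f = 3/77 = 0.039, and a 10-point difference shrinks to 10 × 0.961 = 9.6 points.

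**The case against.** **The case rarely arises.** Under Protocol 6.8.2, a subject who needs another antibiotic for CABP stops study drug. End-of-treatment assessments, including symptoms, are then made at discontinuation (Protocol Table 1 and its footnote d). For an antibiotic at 80 h that assessment would usually fall inside 72–120 h and turn the fallback off. Symptoms are also recorded daily, and in-window telephone assessments count. This stands, and is why the frequency is probably low.

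**The wording has another reading.** The condition that no assessment was completed could mean none in the 72–120 h window. The 80 h antibiotic would then trigger non-response. The SAP does not say which is meant, and on this reading the first subject in the table still meets every responder criterion, so the two lists collide. The wording has to be settled either way.

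**The cut-off is not confined to the fallback.** A subject assessed at 74 h and treated at 80 h is also a responder if there is no later assessment. This is true, but there the response rests on an assessment inside the protocol window. The anomaly here is that one from before the window overrides an event within it.

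**Failures remain visible elsewhere.** They enter the investigator's assessment, the ECR concordance table (SAP 8.5.4.1) and 28-day mortality. These neither isolate fallback subjects nor correct the primary result.

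**Stronger readings that do not hold.** A reader might infer that a death at 80 h is counted as a response. The documents do not support that, because the undated requirement to be alive can still bar it. A reader might also infer that lifting both arms together in itself favours NI to a material degree. Step 6 shows that equal misclassification largely cancels.

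**Conclusion.** The point holds for CABP antibiotics on the literal text of SAP 6.1: a known failure in the protocol window can be classed as a response because an earlier assessment exists. For deaths the finding is a contradiction between the two lists, not a rule that clearly counts the death as a response.

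The size is 0.27 points per subject in one arm. The range of 0.025 to 1.5 points per arm rests wholly on assumed fallback and event rates. The NI conclusion would change only near the boundary, and bias toward NI needs late antibiotic use that differs between arms. The type I figures assume a lift in lefamulin only; they illustrate the mechanism and are not forecasts.

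The correction should still be made before unblinding, because it concerns the primary endpoint, departs from the protocol without being listed, and is cheap.

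**What to change.** In SAP 6.1:

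- State that when no symptom assessment exists in the 72–120 h window, including when the 60 to <72 h fallback is used, death from any cause or a concomitant antibiotic for CABP through 120 hours after the first dose makes the subject a non-responder.
- Define the no-assessment condition as none in the 72–120 h window.
- Date the requirement to be alive, so that the two lists cannot disagree.
- Align the Study Day 5 death limit with 120 h.

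Make the same changes in SAP 6.3.2. List the fallback in SAP 9.0. Add to SAP 8.5.2 a sensitivity analysis that treats fallback-only subjects as indeterminate.

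The cost is a few sentences, a small program change and one table. Planned N (738) and 90% power are unchanged, because 79% is an assumed rate. The observed responder rate may be slightly lower.

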## 6.2 Secondary Efficacy Outcomes

Secondary efficacy outcomes include:

- Percentage of subjects with IACR of success at the TOC Visit in the mITT and CE-TOC Analysis Sets
- Percentage of subjects with ECR of responder in the microITT Analysis Set
- Percentage of subjects with IACR of success at the TOC Visit in the microITT and ME-TOC Analysis Sets
- Proportion of subjects with a by-pathogen microbiologic response of success at the TOC Visit in the microITT and ME-TOC Analysis Sets
- All-cause mortality (ACM) through Day 28 in the ITT Analysis Set

### 6.2.1 Investigator's Assessment of Clinical Response

Clinical response will be assessed by the Investigator at the EOT, TOC and LFU Visits. The IACR at EOT and TOC will be classified as success, failure, or indeterminate according to the definitions in [Table 3](#). Subjects who are deemed to have an IACR of failure at the EOT Visit will not have an IACR performed at the TOC Visit and will be considered to have an IACR of failure at the TOC Visit.

**Table 3. Investigator’s Assessment of Clinical Response at EOT and TOC**

Outcome	EOT and TOC
Success	The subject's clinical signs and symptoms have resolved or improved such that no additional antibacterial therapy is administered for the treatment of the current episode of CABP.
Failure	A subject is a treatment failure if any of the following is met: 
 
• Signs and symptoms of CABP have not resolved, not improved or have worsened such that non-study antibacterial therapy is administered for the treatment of the current episode of CABP.
 
• Measures of inflammation such as temperature or elevated WBC have worsened or failed to improve such that non-study antibacterial therapy is administered for the treatment of the current episode of CABP.
 
• Bacteremia has worsened or failed to improve resulting in administration of non-study antibacterial therapy.
 
• The occurrence of an AE requiring discontinuation of study drug and institution of non-study antibacterial therapy for the treatment of the current episode of CABP.
 
• Death from any cause.
 

Indeterminate	Insufficient information is available to determine success or failure, specifically lost to follow-up.

For subjects who do not have an IACR of failure at the TOC Visit, a determination of clinical response (sustained success, relapse, prior failure or indeterminate) will be made at the LFU Visit as outlined in Table 4. Subjects who are deemed to have an IACR of failure at the TOC Visit will not have an IACR performed at the LFU Visit and will be considered to have an IACR of prior failure at the LFU Visit.

**Table 4. Investigator’s Assessment of Clinical Response at LFU**

Outcome	LFU
Sustained Success	The subject's clinical signs and symptoms remain resolved or further improved such that no additional antibacterial therapy has been administered for the treatment of the current episode of CABP.
Relapse	The subject was a clinical success at TOC, however, any of the following are met: 
 
• Clinical signs and symptoms of CABP have recurred such that additional non-study antibacterial therapy is administered for the treatment of the current episode of CABP.
 
• Measures of inflammation such as temperature or elevated WBC have recurred such that additional non-study antibacterial therapy is administered for the treatment of the current episode of CABP.
 
• Recurrent bacteremia resulting in administration of non-study antibacterial therapy.
 
• Death from any cause.
 

Prior Failure	The subject had an IACR of failure at the TOC Visit.
Indeterminate	Insufficient information is available to determine sustained success or relapse, specifically lost to follow-up.

The secondary efficacy analysis of IACR at the TOC Visit will be conducted in the mITT, CE-TOC, microITT, and ME-TOC Analysis Sets. An additional analysis will be conducted in the microITT-2 and emicroITT Analysis Sets (see Section 6.3). Analyses of IACR at the EOT Visit will be conducted in the mITT, microITT, CE-EOT and ME-EOT Analysis Sets, and analyses at the LFU Visit will be conducted in the mITT, microITT, CE-LFU and ME-LFU Analysis Sets (see Section 6.3). For the analysis of IACR at the EOT and TOC Visits in the mITT, microITT, microITT-2 and emicroITT Analysis Sets, the success rate will be calculated as follows:

$$\frac{\text{Number of subjects who are a success}}{(\text{Number of subjects who are a success} + \text{Number of subjects who are a failure} + \text{Number of subjects with an indeterminate IACR})} \times 100\%$$

For the analysis of IACR at the LFU Visit in the mITT and microITT Analysis Sets, the sustained success rate will be calculated as follows:

$$\frac{\text{Number of subjects who are a sustained success}}{(\text{Number of subjects who are a sustained success} + \text{Number of subjects who are a relapse} + \text{Number of subjects who are a prior failure (carried forward from TOC)} + \text{Number of subjects with an indeterminate IACR})} \times 100\%$$

Subjects with an indeterminate IACR at the EOT, TOC and LFU Visits will be excluded from the analysis of IACR at the EOT, TOC and LFU Visits, respectively, in the CE and ME Analysis Sets. For the analysis of IACR at the EOT and TOC Visits in the CE and ME Analysis Sets, the success rate will be calculated as follows:

$$\frac{\text{Number of subjects who are a success}}{(\text{Number of subjects who are a success} + \text{Number of subjects who are a failure})} \times 100\%$$

For the analysis of IACR at the LFU Visit in the CE-LFU and ME-LFU Analysis Sets, the sustained success rate will be calculated as follows:

$$\frac{\text{Number of subjects who are a sustained success}}{(\text{Number of subjects who are a sustained success} + \text{Number of subjects who are a relapse} + \text{Number of subjects who are a prior failure (carried forward from TOC)})} \times 100\%$$

